#### ADDITIONAL PRINCIPLES FOR MEDICAL RESEARCH COMBINED WITH MEDICAL CARE

The physician may combine medical research with medical care, only to the extent that the research is justified by its potential prophylactic, diagnostic or therapeutic value. When medical research is combined with medical care, additional standards apply to protect the patients who are research subjects.

The benefits, risks, burdens and effectiveness of a new method should be tested against those of the best current prophylactic, diagnostic, and therapeutic methods. This does not exclude the use of placebo, or no treatment, in studies where no proven prophylactic, diagnostic or therapeutic method exists. See footnote

At the conclusion of the study, every patient entered into the study should be assured of access to the best proven prophylactic, diagnostic and therapeutic methods identified by the study.

The physician should fully inform the patient which aspects of the care are related to the research. The refusal of a patient to participate in a study must never interfere with the patient-physician relationship.

In the treatment of a patient, where proven prophylactic, diagnostic and therapeutic methods do not exist or have been ineffective, the physician, with informed consent from the patient, must be free to use unproven or new prophylactic, diagnostic and therapeutic measures, if in the physician's judgement it offers hope of saving life, re-establishing health or alleviating suffering. Where possible, these measures should be made the object of research, designed to evaluate their safety and efficacy. In all cases, new information should be recorded and, where appropriate, published. The other relevant guidelines of this Declaration should be followed.

## Appendix

## Appendix

### CRF ELIGIBILITY

**Inclusion Number:** .....

**Date of the visit :** .....

**Date of Birth:** .....

➤ **Inclusion Criteria (check each point)**

- Female breast cancer patients
- Treated with primary breast conserving surgery for stage I-III invasive adenocarcinoma of the breast or ductal carcinoma in situ (DCIS)
- Age between 40-75 years at time of start radiotherapy
- WHO performance status 0-1
- Planned for radiotherapy alone to the breast with or without the lymph node areas
- Radiotherapy based on planning-CT scan using either 3D-CRT, IMRT, or VMAT/RapidArc
- Written Informed consent

➤ **Non Inclusion Criteria (check each point)**

- Male breast cancer patients
- Neoadjuvant or adjuvant chemotherapy
- M1 disease (metastatic breast cancer)
- Medical history of coronary artery disease and/or myocardial infarction and/or atrial fibrillation
- Previous thoracic or mediastinal radiation
- Contraindications to injection of iodinated contrast such as allergy or renal failure
- Pregnancy or lactation

## Appendix

### CRF CANCER

**Inclusion Number:** .....

**Date of the visit :** .....

**Date of Birth:** .....

• **Left breast**       **Right breast**

• **Date of the surgery :** .....

• **Type of surgery :** breast conserving surgery       mastectomy

• **Axillary lymph node exploration :**

axillary sentinel lymph node biopsy       axillary lymph node dissection

• **Histology :** In situ       invasive

• **Size (mm) :** .....

• **Regional lymph nodes (N)**

**NX** (Regional lymph nodes cannot be assessed (eg, previously removed))

**N0** (No regional lymph node metastasis)

**N1** (Metastasis to movable ipsilateral level I, II axillary lymph node(s))

**N2** (Metastases in ipsilateral level I, II axillary lymph nodes that are clinically fixed or matted or in clinically detected\* ipsilateral internal mammary nodes in the *absence* of clinically evident axillary lymph node metastasis)

**N2a** (Metastases in ipsilateral level I, II axillary lymph nodes fixed to one another (matted) or to other structures)

**N2b** (Metastases only in clinically detected\* ipsilateral internal mammary nodes and in the *absence* of clinically evident level I, II axillary lymph node metastases)

**N3** (Metastases in ipsilateral infraclavicular (level III axillary) lymph node(s), with or without level I, II axillary node involvement, or in clinically detected \* ipsilateral internal mammary lymph node(s) and in the *presence* of clinically evident level I, II axillary lymph node metastasis; or metastasis in ipsilateral supraclavicular lymph node(s), with or without axillary or internal mammary lymph node involvement)

**N3a** (Metastasis in ipsilateral infraclavicular lymph node(s))

**N3b** (Metastasis in ipsilateral internal mammary lymph node(s) and axillary lymph node(s))

**N3c** (Metastasis in ipsilateral supraclavicular lymph node(s))

• **Grade :** Grade 1       Grade 2       Grade 3

• **Vascular invasion :** yes       no

• **Presence of a component in situ :** yes       no

• **Multifocality :** yes       no

• **Her-2** : negative  positive (amplification or overexpression)

• **Oestrogen Receptor**: negative  positive

• **progesterone receptor**: negative  positive

• **Menopause** : No  Yes  Since : .....

• **Hormone therapy** Yes  No

If yes, which one : Tamoxifene  Aromatase inhibitors  Others

Date of the beginning of hormone therapy : .....

• **Date of the beginning of radiotherapy** : .....

• **Irradiation volumes** :

Breast  Chest wall

Nodes : Yes  No

If yes,

Supraclavicular node : Yes  No

Infraclavicular (subclavicular) node : Yes  No

Internal Mammary node : Yes  No

Axillary node: Yes  No

• **Boost** : Yes  No

**Appendix**

**CRF PLANNED RT**

**Inclusion Number:** .....

**Date of the visit :** .....

**Date of Birth:** .....

• **Type of radiotherapy :**

3D-CRT       IMRT       VMAT/RapidArc

• **Breath hold :**

yes       no

• **Boost electrons/photons:**

photons       electrons

Complete :	Dose/fraction	Number of fractions	Total Dose	Comments, if any :
Breast or Chest wall				
Boost				

## Appendix

### CRF RT TOXICITY

**Inclusion Number:** .....

**Date of the visit :**.....

**Date of Birth:** .....

**Precise if it is : during radiotherapy**

**at the end of radiotherapy**

**6 months after the end radiotherapy**

**2 years after the end of radiotherapy**

**Acute toxicity of grade >2 :**

Dermatitis Yes  No

Chest wall/breast pain Yes  No ,

Edema Yes  No ,

Breast and arm Yes  No

Esophagitis Yes  No

**Late toxicity of grade >2 :**

Telangiectasia Yes  No

Fibrosis in boost and out boost area Yes  No

Global cosmetic result Yes  No

Edema breast, edema arm Yes  No

Function of the shoulder Yes  No

Chest wall/breast pain Yes  No

Rib fracture Yes  No

Brachial plexopathy Yes  No

Pneumonitis Yes  No

**Appendix**

**CRF CARDIOLOGY**

**Inclusion Number:** .....

**Date of the visit :** .....

**Visit 1 at baseline**

**Visit at 2 years**

**Date of Birth:** .....

Weight : .....kg

Size : .....m.....

• **Blood Pressure - Hypertension**

Systolic Blood Pressure : .....mmHg

Diastolic blood Pressure : .....mmHg

Treatment  Yes  No

Hypertension:  Yes  No Defined as having Systolic BP > 140 or Diastolic BP > 90 mmHg, or treatment for hypertension

• **Tobacco :**

Non smoker

Former smoker

- Year of beginning: ..... Year of stop : .....

Mean Number of cigarettes/day during the smoking period: .....

Active Smoker

- Age or year of beginning .....

Mean Number of cigarettes/day : .....

• **Diabetes :**

No

Yes  type 1  type2

- Beginning of the diabetes (year) : .....

Actual treatment : .....

• **Cholesterol:**

LDL Cholesterol mg/dL:.....

HDL Cholesterol mg/dL.....

Total Cholesterol mg/dL: .....

Triglycerides : .....

Treatment for hypercholesterolemia (statin) :  Yes  No

SI conversion factors: To convert total, HDL, and LDL cholesterol from mmol/L to mg/dL , divide by 0.0259; triglyceride to from mmol/L to mg/dL , divide by .0113.

• **Fasting glucose** :..... mmol /L

• **Urea**:..... mmol /L

• **Creatinine** : .....  $\mu$ mol/L

• **eGFR (MDRD formula)** : ..... mL/min per 1.73 m^2

-> < 50 ml/min/1.73 m^2  Yes  No (if yes, the patient should be excluded of the study (exclusion criteria) )

•  $\beta$  HCG ..... mmol /L

• **Electrocardiogram (ECG)**

Atrial fibrillation detected  Yes  No (if yes, the patient should be excluded of the study (exclusion criteria) )

ECG sign of myocardial Infarction  Yes  No if yes, the patient should be excluded of the study (exclusion criteria) )

**Other medical cardiology treatment**  Yes  No  
If yes, precise in clear: .....

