## **Exclusion criteria**

- Atrial fibrillation detected during electrocardiogram before radiotherapy
- Abnormal echocardiography before radiotherapy defined as: LVEF<50%; longitudinal strain  $\leq$  -16%; longitudinal strain rate  $<$ -1%, and/or abnormal wall motion
- Presence of myocardial infarction detected during MRI before radiotherapy
- CTCA or cardiac MRI results before radiotherapy requiring revascularisation

▶ See CRF ELIGIBILITY in appendix for further details

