### **11.4. Benefits and risks assessments, group relatedness**

Participation in this study does not involve any additional risk to patients, besides the risk incurred by additional MRI and CT-scans. Patients will undergo 2 extra CT-scans. For CT, patient is subject to a scanning X-ray beam. The latest techniques in CTCA achieve very low levels of radiation (below 4mSv) , equivalent to one to two years of natural background radiation (average of 2.4 mSv / year), considered acceptable for exam screening for which the radiation-induced risk should be minimal or nil. Additionally, compared to the radiation dose of the treatment the dose of the extra CT scans is very low and the risks therefore are negligible and the burden low.

Participation in this study may have benefits. When cardiac imaging reveal severe abnormal findings, such as the presence of severe coronary artery disease which may require a revascularization or specific treatment due to the presence of a myocardial infarction, patients even in absence of symptoms will be excluded of the present study and referred to the cardiologist . In absence of severe coronary artery disease, all results of cardiac imaging will be blinded to the medical staff in order to avoid changes in medical treatment likely to mask effects of XRay radiation which the main objective of the present study.

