**Specific part of CRF at Visit 2 at 2 years follow up:**

The medical cardiology treatment has been introduced or changed since V1 at inclusion  
 Yes  No

If yes precise the date : .....

Modification of the ECG compared to the ECG at inclusion  Yes  No

Occurrence of Cardiovascular Event since inclusion  Yes  No

Occurrence of cardiac symptoms,  Yes  No

▶ If Yes to event or symptoms,  
please specify the date and type of event or symptoms (dyspnea, palpitation, chest pain...), death, myocardial infarct, heart failure, hospitalization for cardiac diseases, atrial fibrillation or other significant arrhythmia, stroke etc...

.....  
.....

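### Section 4 limits every exclusion criterion to findings before radiotherapy, but section 11.4 and the cardiology, CT and MRI forms order exclusion with no time limit, although the examinations are repeated after radiotherapy

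*Combined protocol and SAP*

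**What the plan says.** The exclusion list in section 4 has four items, each tied to the period before radiotherapy. Three concern findings that recur elsewhere: "Atrial fibrillation detected during electrocardiogram before radiotherapy", "Presence of myocardial infarction detected during MRI before radiotherapy" and "CTCA or cardiac MRI results before radiotherapy requiring revascularisation". The fourth is an abnormal echocardiogram before radiotherapy.

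Section 11.4 discusses severe abnormal imaging findings (severe coronary disease that may need revascularisation, or infarction) and says that "patients even in absence of symptoms will be excluded of the present study and referred to the cardiologist". It gives no visit.

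CRF CARDIOLOGY has one body with boxes for baseline and for 2 years. In that shared body the instruction "if yes, the patient should be excluded of the study (exclusion criteria" stands next to eGFR below 50, next to atrial fibrillation on ECG, and next to "ECG sign of myocardial Infarction". A later block, "Specific part of CRF at Visit 2 at 2 years follow up", asks for "Occurrence of Cardiovascular Event since inclusion" and lists infarction and atrial fibrillation among the examples.

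The local CT form excludes a woman from study and follow-up after a revascularisation. The local MRI form excludes her if she needed vascularisation or if an infarction is detected. Neither form has a visit box. Under section 7.4 and the flowchart, ECG and CT are repeated at 24 months and MRI at 6 and 24 months.

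**The concern.** In a cohort set up to detect cardiovascular change within two years of radiotherapy, baseline exclusions define the population. Exclusions triggered at 6 or 24 months select on the outcome. A centre completing the cardiology form at 2 years, or the MRI form at 6 months, finds an order to exclude and nothing limiting it to baseline. If some centres follow it and others follow section 4, women with the same finding will be handled differently across sites.

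Two analyses are exposed. The primary endpoint in section 3.2.1 needs strain at baseline and at 24 months. Stage III in section 9.3 needs a cardiac toxicity outcome, and infarction or atrial fibrillation after radiotherapy are natural candidates for it.

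**Working it through.** The plan gives no figure to reproduce here, so the check sets the passages side by side.

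**Step 1. Timing of each exclusion order.**

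| Place | Trigger | Time limit stated | Same examination or form used after radiotherapy |
|---|---|---|---|
| Section 4, four items | AF on ECG; abnormal echo; infarction on MRI; CT or MRI result requiring revascularisation | Before radiotherapy, all four | not applicable |
| Section 11.4 | Severe coronary disease or infarction on imaging | None | CT 24 months; MRI 6 and 24 months |
| CRF CARDIOLOGY, shared part | eGFR below 50 | None | 2-year visit |
| CRF CARDIOLOGY, shared part | AF on ECG | None | ECG 24 months |
| CRF CARDIOLOGY, shared part | ECG sign of infarction | None | ECG 24 months |
| Local CT form | Revascularisation | None | CT 24 months |
| Local MRI form | Vascularisation required, or infarction | None | MRI 6 and 24 months |
| Local ECHO-ST form | Abnormal echo | Before radiotherapy | ECHO-ST 6 and 24 months |

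Section 4: 4 of 4 time-limited. Outside section 4: 1 + 3 + 1 + 1 + 1 = 7 orders, of which 6 are untimed. Counting cardiac triggers only (without eGFR), 5 of 6 are untimed.

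**Step 2. Do the untimed orders merely repeat section 4?** Only in part.
- AF on ECG and infarction on MRI match section 4 items, apart from the missing time limit.
- An ECG sign of infarction is labelled an exclusion criterion on the form, but section 4 lists infarction only as an MRI finding or as medical history.
- eGFR below 50 carries the same label. Section 4 has only renal failure, as a contraindication to iodinated contrast in the non-inclusion list, with no eGFR threshold.
- Revascularisation is worded in several ways: results requiring it (section 4), disease that may require it (section 11.4), required vascularisation (MRI form) and revascularisation done (CT form).

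**Step 3. Is there an internal conflict at 2 years?** Yes. The shared part of CRF CARDIOLOGY orders exclusion for AF and ECG-detected infarction. The 2-year part of the same form collects infarction and AF as events since inclusion. The form does not say which use applies to a finding made at that visit.

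**Step 4. What could be lost if the orders were applied after radiotherapy?**
- Infarction on the 6-month MRI: the woman leaves before the 24-month strain measurement. MRI is optional (section 7.2), so this path exists only for women who have it.
- AF or a sign of infarction on the 24-month ECG: sections 1.6 and 8 place ECHO-ST after the ECG, so strain at that visit could be lost.
- Revascularisation after the 24-month CT: the order of CT and ECHO-ST within that visit is not stated, so loss of the strain value cannot be inferred. Whether the woman stays in the analysis remains open.

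**Step 5. Does the analysis plan settle it?** No. Section 9.3 defines no analysis set and gives no rule for women excluded after radiotherapy. Section 12.7 keeps data for twenty years, which concerns storage rather than analysis.

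**The case against.** The strongest reply is that baseline-only use is the natural reading. The cardiology form's label points back to the exclusion criteria, which section 4 limits to before radiotherapy. The echocardiography form, used at three visits, states that limit. The 2-year block records infarction and AF as data, which makes little sense if those women are removed at that visit. The CT form speaks of leaving follow-up, and at 24 months none is left. Section 12.4 has monitors check eligibility against the protocol. All of this stands as evidence of intent. It does not supply the missing words: the echocardiography form shows that the authors wrote the limit when they meant it, and two of the three labelled triggers on the cardiology form have no counterpart in the list to which the label refers.

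The consequences may also be small. Section 2.1 places clinically significant complications many years after radiotherapy. The Stage II mixed models can use baseline and 6-month values when the 24-month value is absent. Section 12.2 requires the reason for withdrawal to be recorded, and AF found on the 24-month ECG would still be on the form. These points reduce the harm but do not remove selection on the outcome.

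A reader might infer that the sponsor plans to exclude women after radiotherapy so that treatment does not mask radiation effects. Section 11.4 does not say this. It gives masking as the reason for blinding results to medical staff, not as a reason for exclusion. A reader might also infer bias towards no effect or a material loss of power. The documents give no rate of AF, infarction or revascularisation within 24 months and no strain values for such women, so neither inference is supported.

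**Conclusion.** The point holds as an inconsistency that should be fixed. Section 4 is uniformly time-limited, while six of the seven exclusion orders outside it are not, and the examinations behind them are repeated after radiotherapy. Followed literally, the orders remove women because of the findings under study; followed as probably intended, they do not. The finding is therefore conditional: it shows that the text permits selection on outcome, not that such selection is planned or will occur.

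The size and direction of any effect on the primary endpoint or on Stage III cannot be derived from the documents. The conclusion rests on the wording of the forms and on section 9.3 being silent about women excluded after radiotherapy. It needs no assumption about event rates.

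**What to change.** Reconcile section 4, section 11.4, both parts of CRF CARDIOLOGY and the local CT and MRI forms by naming the visit at which each exclusion applies, consistent with the limit already in section 4. Reconcile the eGFR and ECG-infarction orders on the cardiology form with the non-inclusion and exclusion lists, and align the differing wordings on revascularisation.

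Add to section 9.3 that women with such findings after radiotherapy are not removed from the cohort or the analysis because of them, and that their collected data and events are kept. Strain measured after revascularisation or new cardiac treatment may reflect that treatment, so simply pooling it is not enough: specify a sensitivity analysis that examines those measurements separately. The 2-year part of CRF CARDIOLOGY already asks whether cardiac treatment was introduced or changed, and when.

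The cost is a clause in section 11.4 and on three forms, the matching edit to section 4, and two or three sentences in section 9.3. No examination or visit is added, and referral and clinical care are unaffected.

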**Specific part of CRF at Visit 2 at 2 years follow up:**

The medical cardiology treatment has been introduced or changed since V1 at inclusion  
 Yes  No

If yes precise the date : .....

Modification of the ECG compared to the ECG at inclusion  Yes  No

Occurrence of Cardiovascular Event since inclusion  Yes  No

Occurrence of cardiac symptoms,  Yes  No

▶ If Yes to event or symptoms,  
please specify the date and type of event or symptoms (dyspnea, palpitation, chest pain...), death, myocardial infarct, heart failure, hospitalization for cardiac diseases, atrial fibrillation or other significant arrhythmia, stroke etc...

.....  
.....

## Appendix

### LOCAL CRF ECHO-ST

**Inclusion Number:** .....

**Date of the visit** : .....

**Date of Birth:** .....

Name and version of the of the ultrasound system:

- General Electric Health Care , version:
- Philips, version:
- Siemens, version:
- Toshiba, veesion
- Other to precise:

Precise if it is : before radiotherapy

6 months after the end radiotherapy

2 years after the end of radiotherapy

- Global longitudinal strain: .....
- Segmental longitudinal strain (Segment 1 to 16) : .....
- Global longitudinal strain rate: .....
- Segmental longitudinal strain rate (Segment 1 to 16) : .....
- Global radial strain : .....
- Segmental radial strain (Segment 1 to 16) : .....
- Global radial strain rate: .....
- Segmental radial strain rate (Segment 1 to 16) : .....
- Left ventricular ejection fraction using Simpson's biplane method: .....
- Left ventricular end-diastolic volume using Simpson's biplane method: .....
- Left ventricular end-systolic volume using Simpson's biplane method: .....
- Left-ventricular end-diastolic diameter using M-mode: .....
- Left ventricular mass measured according ASE/EAE guidelines: .....
- E/A wave ratio : .....
- E/Ea wave ratio (lateral annulus) : .....
- TAPSE (tricuspid annular plane systolic excursion) : .....
- Tricuspid annular S wave : .....
- Pulmonary artery systolic pressure (based on the peak tricuspid regurgitation velocity estimate and by assuming a right atrial pressure of 5 mmHg) : .....
- Left ventricular outflow tract diameter: .....
- Left ventricular outflow tract velocity time integral: .....
- Heart rate: .....
- Cardiac output measured by multiplying heart rate by stroke volume: .....

**In case of abnormal echocardiography before radiotherapy defined as: LVEF<50%; longitudinal strain  $\leq$  -16%; longitudinal strain rate <-1%, and/or abnormal wall motion, the patient should be excluded of the study (exclusion criteria )**

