## 3.2. Endpoints

### 3.2.1. Primary endpoints

The primary endpoints are defined as a mean decrease in Global Longitudinal Strain or Global Longitudinal Strain Rate, determined by cardiac ECHO-ST, of at least 2.5% between baseline and 24 months after RT (*Erven et al, Int J Radiation Oncol Biol Phys, 2012; Lo et al, In J Radiation Oncol Biol Phys, 2015*).

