### 9.2. Sample Size

The sample size was based on a statistical power of 80%, an alpha-risk of 5%, the definition of the primary endpoint (a decrease in the global and segmental longitudinal strain or strain rate of at least 2.5%) and baseline measurements hypothesis (mean global longitudinal strain before RT : -16.5%  $\pm$  2.1% from Dalen et al, European Journal of Echocardiography : the Journal of the Working Group on Echocardiography of the European Society of Cardiology. 2010) Considering paired test for comparisons, but also possible lost to follow-up due to death or other reason, the inclusion of 250 women is necessary for EARLY-HEART study.

Centre	Recruitment rate per month	Total number of patients to recruit in 1 year
IRSN	4.2	50
UMCG	5	70
TUM-MED	4.6	55
CCUL	2.1	25
ICO	4.2	50
Total		250

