## **12.3. Dose data repository; storage of DICOM data**

The MEDIRAD-ENACT database of partner UMCG will be used for MEDIRAD EARLY-HEART to enable integrated data-collection, quality control and management for the clinical study on low-dose radiation-induced early cardiovascular changes after BC therapy.

A centralised integrated imaging and dose repository will be set up to serve the needs of the research and studies carried out in MEDIRAD based on anonymised data (Work Package 2.4.1 ).

All participating centres will transfer relevant DICOM-data (i.e. imaging, planning-CT scans, RT-STRUCT, RT-DOSE, CTCA and MRI (all native images from all series with and without additional image (including additional image (T1 and T2 mapping, aortic 3D images... ))) to the ENACT data bank managed by UMCG. The ENACT environment provides easy and secure upload of (image/DICOM) data to a central archive located at the UMCG. De-identification of the (image) data will be performed at the site of origin before sending according to a de-identification strategy. After upload, researchers involved in the reading of the imaging data will be provided access to the ENACT environment using a virtual workspace with two-way authentication (login + SMS-token). The virtual workspace can be accessed from any location and from different platforms (Windows/Apple/Linux) allowing selection of expert readers to perform the reading regardless of their location. Each reader will be provided with an identical workspace with the same software tools and imaging data, no subsequent transfer of (imaging) data is needed except a secured transfer of all anonymized Cardiac CT and Cardiac MR from the ENACT database to Université Paris Descartes which is Core center for reading all CTCA and Cardiac MRI of patients included in

EARLY HEART Study (Responsible party: [name], Univ Paris Descartes). Indeed for analysis of cardiac imaging, ENACT transfer of DICOM anonymized images will be required by the core lab in order to use research softwares dedicated to specific tasks and softwares routinely used by expert readers. Electronic CRF will be filled by the core lab during such analysis.

Within the ENACT environment automated segmentation of all cardiac structures (including coronary arteries) is performed to ensure uniformity of the segmentation procedure between centres. In addition, storage of all DICOM-data in ENACT will enable co-registration of the different imaging data.

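### Treating staff are kept from the imaging results, but no image reader is masked to visit, treated side or dose; the gap matters most for the locally recorded strain endpoint

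*Combined protocol and SAP*

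**What the plan says.** - **Who is blinded.** Section 11.4 states that, where no severe coronary disease is found, "all results of cardiac imaging will be blinded to the medical staff in order to avoid changes in medical treatment". The CTCA appendix likewise keeps the calcium score and remaining CT results from the clinicians. Both provisions concern the treating side, and Section 11.4 gives the aim as preventing treatment changes.
- **Primary endpoint.** Section 3.2.1 defines it as a mean fall in global longitudinal strain or strain rate, "determined by cardiac ECHO-ST, of at least 2.5% between baseline and 24 months after RT".
- **Where strain is recorded.** The appendix form LOCAL CRF ECHO-ST takes the visit date, a visit box ("Precise if it is : before radiotherapy", 6 months, 2 years) and the strain values. The baseline values on it also serve the echo exclusion criterion.
- **Who reads CT and MRI.** Section 12.3 sends these two modalities to one core lab and adds: "Electronic CRF will be filled by the core lab during such analysis". Echo is not on that list. The image quality check in Section 12.5 collects example CT and MR scans only.
- **De-identification.** Section 12.3 removes patient identity at the site before upload. It does not mention visit, side or dose.

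**The concern.** The main conclusions rest on three comparisons: change within each woman over time (Sections 9.2 and 9.3, Stage I), left- versus right-sided treatment (Section 1.7), and dose-response (Section 9.3, Stage II). Every woman is irradiated, so nothing in the before-after comparison absorbs a drift in how follow-up images are measured. A reader who knows a loop was recorded after radiotherapy and expects worse strain can produce part of the expected change. That expectation is set out in Section 2.1, which reports an average strain fall of 5% in the first year and a left-right difference.

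A shift common to all women at follow-up would bias the before-after result but would largely cancel in the left-right and dose-response comparisons. Those are biased only if the reader also knows side or dose. A larger sample removes neither problem. It makes a given systematic shift more likely to reach significance.

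**Working it through.** **Inputs from Section 9.2:** baseline strain mean 16.5 in absolute value; SD 2.1; power 80%; alpha 5% (taken as two-sided); 250 women; "Considering paired test for comparisons". Not given: the within-woman correlation ρ, the dropout rate, and whether 2.5% is relative or in strain points. I vary all three.

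**Step 1. Which reading of 2.5% fits 250?**

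SD of change = 2.1 × √(2(1 − ρ)); n = ((1.960 + 0.842) × SD of change / δ)².

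- Relative: δ = 0.025 × 16.5 = 0.4125 points. With ρ = 0.5 the SD of change is 2.1, and n = (2.802 × 2.1 / 0.4125)² ≈ 203.4, so 204 pairs. For other ρ: 407 (0), 245 (0.4), 123 (0.7), 82 (0.8).
- Absolute: δ = 2.5 points. With ρ = 0.5, n = (2.802 × 2.1 / 2.5)² ≈ 5.5, so 6 pairs. Over ρ = 0 to 0.8, n runs from 12 down to 3.

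The plan's 250 is therefore not reproduced from stated inputs alone. It is compatible with the relative reading under added assumptions, for example ρ = 0.5 and about 18% dropout (1 − 204/250 = 0.184). The absolute reading cannot explain it. The planned Wilcoxon test changes little: at efficiency 0.955 for normal data, 204/0.955 = 213.6, so 214.

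**Step 2. An assumed reader shift against the target.**

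| Assumed mean shift at follow-up | Share of 0.4125 (relative) | Share of 2.5 (absolute) |
|---|---|---|
| 0.2 points | 0.2/0.4125 = 48% | 0.2/2.5 = 8% |
| 0.4 points | 0.4/0.4125 = 97% | 0.4/2.5 = 16% |

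**Step 3. Chance of a significant before-after change when the true change is zero.**

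With shift b and SE = SD of change / √n, a two-sided 5% paired test against zero rejects with probability 1 − Φ(1.96 − b/SE) + Φ(−1.96 − b/SE).

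Example: n = 250, ρ = 0.5, b = 0.2. SE = 2.1/√250 = 0.133; b/SE = 1.51; probability 0.325.

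| Assumed shift b | Range over n = 204 to 250, ρ = 0.5 to 0.8 |
|---|---|
| 0.05 points | 6–9% |
| 0.1 points | 10–22% |
| 0.2 points | 27–66% |
| 0.4125 points | 80% to over 99% |

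These probabilities depend on n and the SD of change, not on how 2.5% is read. That reading decides how large the shift is beside the change the study regards as important.

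**Step 4. What the documents show each reader knows.**

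- Visit: on the echo form with the strain values. For CT and MRI, neither disclosed nor masked in the text.
- Side: not on the echo form; it is on CRF CANCER.
- Dose: not on the echo form; the prescription is on CRF PLANNED RT.
- Earlier strain values: not on the echo form, and no section says the same person reads all visits.

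**The case against.** **The visit box proves nothing by itself.** Any case report form must identify its visit. This stands. The defect is that the measurer is not masked and echo has neither a core lab nor a masked re-read.

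**Readers do not demonstrably know side, dose or earlier values.** This also stands. A reader might infer that the core lab sees the dose plan, because the repository holds RT-STRUCT and RT-DOSE files and Section 12.3 says "Each reader will be provided with an identical workspace with the same software tools and imaging data". The same section makes an exception for this core lab: it receives a transfer, and only cardiac CT and cardiac MR are named in it. A reader might also infer that the echo reader knows the treated side and holds the baseline value. No section says so, and Section 11.4 arguably restricts access to baseline results. For side and dose the point is only that masking is not stated.

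**Measurement is partly automated.** The plan calls the speckle tracking automated, and the main MRI endpoint is a quantitative T1 value. Both may limit reader influence. The plan does not say that they remove it, and scoring plaque and stenosis by coronary segment still needs judgement.

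**The study has internal contrasts.** Left versus right and dose-response give some protection against a shift common to all women. They do not protect the before-after primary endpoint.

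**The shift sizes are assumed.** Correct. The documents give no reader-error figure.

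**Conclusion.** The concern holds in a limited form. The plan masks the treating staff and does not state any masking of image readers to visit, side or dose. The exposure is greatest for strain, which is recorded locally, falls outside the CT and MRI core lab, and is compared before and after without an unirradiated control. A shift by visit would be indistinguishable from a radiotherapy effect. A shift by side or dose would bias the other two analyses only if the reader knows these.

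The size is unknown. Under the relative reading of 2.5%, an assumed shift of 0.2 points is about half the target; under the absolute reading it is 8%. The false-positive range for that shift, 27–66%, rests on assumed ρ of 0.5 to 0.8, 204 to 250 pairs and a test against zero. A reader might go further and infer that readers are biased, or that a positive result would be an artefact. The documents support neither. They show an avoidable route for bias that should be closed before follow-up images are read.

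**What to change.** **Section 12.3, CT and MRI.** State that the core lab scores under visit-neutral codes, with scan dates and treated side withheld, and with baseline and follow-up in random, unlabelled order (shown together if the reading needs it). Confirm that dose files are not supplied. The local readings already used for clinical findings are unaffected.

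**ECHO-ST appendix.** Keep the local baseline reading for eligibility only. For the endpoint analysis, have the existing readers measure stored loops from all three visits (baseline, 6 and 24 months) under codes and in random order, without visit date, side, dose or earlier values. The coordinator links codes to visits. Baseline loops must be included: if only follow-up loops are coded, the reader knows every coded loop is post-treatment and the before-after bias remains. State that loops are stored. Section 12.1 already lists echo among the imaging data, and Stage II needs the strain curves.

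**Cost.** Coding and coordinator time, plus one repeat measurement of the stored baseline loops. No new staff or patient procedures are needed. Masking will be imperfect where the reader also scanned the woman.
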